10.3.3 Other Adverse Reactions

Pooling the adverse event data from the TRA 2°P TIMI 50 study¹² (13,186 patients) and TRA•CER (Thrombin Receptor Antagonist for Clinical Event Reduction in Acute Coronary Syndrome) study¹¹ (6,446 patients), the incidence of the adverse events was as shown in Table 1.

Table 1. Percentage of patients reporting non-haemorrhagic adverse events

	Vorapaxar N= 19,632	Placebo N= 19,607
Anemia	5%	4%
Depression	2.4%	2.1%
Rashes, Eruptions and Exanthemas	2.2%	2.0%

Less common adverse reactions (occurred at a rate of less than 2% in those patients taking vorapaxar but at least 40% greater rate than placebo) were iron deficiency, retinopathy or retinal disorder and diplopia / oculomotor disturbance.

10.4 Discontinuation of study treatment

In general terms, all randomised study participants should aim to take the study treatment as per protocol. However, reasons for either temporarily or permanently ceasing study treatment include:

- Disease progression requiring medical intervention
- Surgical intervention
- Administration of prohibited therapy
- Investigator or participant wish to stop therapy
- Occurrence of unacceptable adverse drug reactions

Participants MUST be discontinued from study treatment if there is any clinical adverse event, laboratory abnormality or intercurrent illness that in the opinion of the investigator indicates that continued treatment with study therapy is not in the best interest of the participant.

11.0 Adverse Event Recording & Reporting

11.1 Adverse Events

The definition of an adverse event is any untoward medical occurrence in a participant administered with a pharmaceutical product which does not necessarily have a causal relationship with the product. Where adverse events are related to the drug, they may be referred to as Adverse Drug Reactions.

Adverse events and adverse drug reactions may occur in the course of this study and within the specified follow-up period. These events may also occur in screened participants during the screening period prior to

randomisation as a result of protocol-specified interventions. All such events will be recorded at each study visit on the adverse event case report form.

In this study we will be collecting all grade (grade 1-4) clinical adverse events. As a general rule, isolated laboratory abnormalities in the absence of clinical symptoms and/or signs should not be captured as adverse events. If the laboratory event becomes clinically significant, then the resulting clinical event should be reported as an adverse event (e.g. low haemoglobin should be reported as anaemia).

Pre-existing conditions or diseases that occur during the study (e.g. seasonal allergies, asthma or recurrent headaches) should not be considered as adverse events unless they change in frequency or severity. In this study we will be collecting all grade (grade 1-4) clinical adverse events. If known, the diagnosis of the underlying illness or disorder should be recorded, rather than its individual symptoms.

11.1.1 Reporting of Adverse Events

Timely and complete reporting of all AEs assists in identifying any untoward medical occurrence, thereby allowing: (1) protection of safety of study subjects; (2) a greater understanding of the overall safety profile of the study drugs; (3) recognition of dose-related study drug toxicity; (4) appropriate modification of study protocols; (5) improvements in study design or procedures; and (6) adherence to worldwide regulatory requirements.

The collection of non-serious AE information should begin at initiation of study drugs. AEs may be either spontaneously reported or elicited during questioning and examination of a participant. All identified AEs must be recorded in the participant's medical notes immediately and entered on the AE page of the eCRF within 1 week of the study visit at which they were reported. If known, the diagnosis of the underlying illness or disorder should be recorded, rather than its individual signs or symptoms.

Participants experiencing AEs that cause interruption or discontinuation of study drugs, or those experiencing AEs that are present at the end of their participation in the study should receive follow-up as appropriate. If possible, report the outcome of any AE that caused permanent discontinuation or that was present at the end of the study particularly if the AE was considered by the investigator to be certainly, probably, or possibly related to the study drugs.

Non-serious AEs should be followed to resolution or stabilisation at or until the end of the study, and reported as SAEs should they become serious.

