Study procedures Participants will be seen one week after randomisation and then at weeks 4, 8 and 12 (phase 1). At the week 12 visit, patients will not be dispensed any study treatment. In phase 2 all study treatment will stop for 6 weeks. At week 18 patients

will be seen for a final study visit.

Procedures include;

1. Informed consent
2. Medical and HIV history
3. Vital Signs (height, weight and sitting blood pressure)
4. Symptom directed physical exam
5. Blood sample collection for local laboratory analysis;
 - D-dimer (screening only for eligibility purposes)
 - Serum or urine pregnancy test
 - Virology: HIV-1 RNA measured using assays with lower limit of detection of at least 50 copies/mL
 - Haematology: full blood count
 - Fasted lipids
 - Biochemistry: Urea, Electrolytes, Creatinine, Liver Function Tests
 - Immunology: CD4+, CD8+ T cell count
6. Blood sample collection for storage and central laboratory analysis;
 - Coagulation / Immune Activation: D-dimer, IL-6, Hs-CRP
7. Blood sample collection for storage and central laboratory analysis (exploratory analyses);
 - Virology: cell associated HIV RNA/DNA, ultrasensitive HIV plasma viral load
 - Immunopathogenesis: ADCC Antibody, NK cell activation, T-cell activation markers, plasma markers of monocyte activation (sCD14, sCD163) and PAR-1 expression (PAR-1 to be analysed on fresh whole blood collected from a subset of participants from sites with capacity to perform this assay in real time)
8. Collection of AEs (including SAEs regardless of relationship to study drug)
9. Collection of concomitant medications

Statistics**Statistical analysis**

Primary analyses will compare the two randomised arms in an intention to treat manner once all patients have completed follow up. Secondary analyses will exclude data in patients who cease study drug. There will be no adjustment of analyses for multiple comparisons.

The primary endpoint will be mean changes in log₁₀ d-dimer levels from baseline at weeks 8 and 12. The proportion of patients with d-dimer < 165 ng/mL (0.165 mg/L) will also be summarised.

Formal analyses will compare the randomised treatment arms in terms of mean differences in changes in log₁₀ d-dimer at week 8 and week 12 using repeated

measures regression methods.

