2.0 Study Flow Chart: Time and events schedule

Study Phase	Screening	Randomisation	Phase 1				Phase 2	
Study week number ^c	SCRN ^a	0 ^b	1	4	8	12	13-17 No study drug	18
Clinical Assessments								
Informed consent	•							
Medical and HIV history	•							
Interim history, AEs assessment and concomitant medication		•	•	•	•	•		•
Targeted physical examination (symptom directed)	•	•	•	•	•	•		•
Vital Signs ^d		•	•	•	•	•		•
Dispense study medication		•		•	•			
Real time local laboratory assessments								
Biochemistry ^e	•	•				•		•
Liver function ^f	•	•				•		•
Haematology ^g	•	•	•	•	•	•		•
Fasted lipids ^h		•						
CD4+ and CD8+ T cell (absolute and %) ⁱ	•	•	•	•	•	•		•
Virology: plasma HIV-1 RNA ^j	•	•	•	•	•	•		•
d-dimer	•							
Pregnancy test ^k	•	•		•	•	•		•
Storage samples for central laboratory analysis								
D-dimer		•	•	•	•	•		•
Hs-CRP		•	•	•	•	•		•
IL-6		•	•	•	•	•		•
Storage samples for central laboratory analysis (exploratory analysis)								
Ultrasensitive plasma viral load		•				•		•
T cell activation marker		•	•	•	•	•		•
ADCC Antibody/ NK cell function		•	•	•	•	•		•
PAR-1 expression ^l		•	•			•		•
Plasma markers of inflammation (sCD14, sCD163)		•				•		•

a All screening assessments are to be completed within 14 days prior to randomisation;

b All randomisation (week 0) assessments should be completed before the participant commences study drugs. Study drug should commence within 1 day of randomisation;

c Study Week Number: All efforts should be made to schedule visits in keeping with the proposed week numbers. Phase 1: week 1 to be conducted within 13 days of randomisation, weeks 4, 8 and 12 to be done +/- 2 weeks of scheduled visit date. Phase 2: week 18 to be conducted within + 2 weeks of scheduled visit date.

d Vital Signs: Sitting blood pressure (all visits), height (week 0 only) and weight (week 0 and week 18 only);

e Biochemistry: electrolytes (sodium, potassium, calcium, bicarbonate, chloride, phosphate), creatinine, urea;

f Liver Function test: ALT and AST;

g Haematology: haemoglobin, white blood cells, neutrophils, lymphocytes, platelets to be done (day 0 and week 12 to be done as standard of care). Haemoglobin to be tested at the time of any clinically significant bleeding event (clinical judgement to be used);

h Fasting lipid parameters includes: total cholesterol, HDL cholesterol, calculated LDL cholesterol and triglycerides;

i CD4+ and CD8+ cell counts: Day 0 and week 12 to be done as standard of care;

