11.4.1 Reporting of SNAEs and AIDS defining illnesses

All SNAEs and AIDS defining illnesses must be reported to the Kirby Institute as per SAE reporting outlined in section 11.2.1. Details of how to report these will be outlined in the MOOP.

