18.0 Data Safety and Monitoring Board (DSMB)

The DSMB will be accountable to the PSC and will undertake independent review of protocol-specified and ad hoc interim analyses if required. The DSMB will be composed of individuals neither directly associated with the study nor employees of any of the organisations responsible for the conduct of the research. The study biostatistician will be an ex officio member of the DSMB. The primary focus of the reviews undertaken by the DSMB will be safety. The first scheduled review will take place after 20 patients have completed 6 weeks of treatment with further reviews scheduled every 8 weeks thereafter. For ad hoc reviews an interim analysis would be prompted when four (4) BARC type 2 events or one (1) BARC type 3 event are reported. During the ad hoc review and until the PSC has received and acted upon a DSMB recommendation, patient recruitment will be paused but randomised patients will continue study treatment. The terms of reference and operating

guidelines of the DSMB will be drafted by the study biostatistician (as documents separate to the Protocol) and finalised in collaboration with the DSMB prior to the commencement of the study.

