Appendix 2: Bleeding Academic Research Consortium (BARC) Definitions for Bleeding Events

Type 0	no bleeding
Type 1	bleeding that is not actionable and does not cause the patient to seek unscheduled performance of studies, hospitalization, or treatment by a healthcare professional; may include episodes leading to self-discontinuation of medical therapy by the patient without consulting a healthcare professional
Type 2	any overt, actionable sign of haemorrhage (eg, more bleeding than would be expected for a clinical circumstance, including bleeding found by imaging alone) that does not fit the criteria for type 3, 4, or 5 but does meet at least one of the following criteria: (1) requiring nonsurgical, medical intervention by a healthcare professional, (2) leading to hospitalization or increased level of care, or (3) prompting evaluation
Type 3	
Type 3a
 
 Overt bleeding plus hemoglobin drop of 3 to <5 g/dL* (provided hemoglobin drop is related to bleed) Any transfusion with overt bleeding 
Type 3b
 
 Overt bleeding plus hemoglobin drop ≥ 5 g/dL* (provided hemoglobin drop is related to bleed) Cardiac tamponade Bleeding requiring surgical intervention for control (excluding dental/nasal/skin/hemorrhoid) Bleeding requiring intravenous vasoactive agents 
Type 3c
 
 Intracranial hemorrhage (does not include microbleeds or hemorrhagic transformation, does include intraspinal) Subcategories confirmed by autopsy or imaging or lumbar puncture Intraocular bleed compromising vision

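### The recruitment pause counts reported BARC type 2 bleeds, but the protocol gives a non-serious one no sponsor deadline except routine eCRF entry after a study visit

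*Protocol*

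**What the plan says.** The trigger is in Protocol section 18.0: "an interim analysis would be prompted when four (4) BARC type 2 events or one (1) BARC type 3 event are reported". While the review runs, "patient recruitment will be paused but randomised patients will continue study treatment". The count is therefore of bleeds reported, not of bleeds that have occurred.

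Under Appendix 2 an overt, actionable bleed is type 2 if it falls short of types 3 to 5 and meets any one of three criteria: "requiring nonsurgical, medical intervention by a healthcare professional, (2) leading to hospitalization or increased level of care, or (3) prompting evaluation". Only the second involves a hospital stay, and an increased level of care also satisfies it. The SAE definition in section 11.2 asks for an in-patient stay of at least 24 hours, a threat to life, disability, or a judgement that the event is medically important. A type 2 bleed can fall outside all of these.

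For adverse events in general, section 11.1 says "All such events will be recorded at each study visit on the adverse event case report form". Section 11.1.1 wants them in the medical notes at once and "entered on the AE page of the eCRF within 1 week of the study visit at which they were reported". SAEs go to the coordinating centre within 24 working hours (section 11.2.1).

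The faster route is extended by name to other categories. Section 11.4.1 states: "All SNAEs and AIDS defining illnesses must be reported to the Kirby Institute as per SAE reporting outlined in section 11.2.1". Pregnancy (11.5) and overdose (11.6) have 24-hour reports of their own. Bleeds are not on that list. Section 10.3.2 deals with haemoglobin testing, study drug and site follow-up after a bleed, but sets no notice to the sponsor. SAP section 5.2 covers only how bleeds are summarised.

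**The concern.** Bleeding is the main risk the protocol names, and this is its numerical rule for reacting to accumulating non-fatal bleeds. Such a rule is only as fast as the reports that feed it. As written, a site may know of a type 2 bleed for weeks before any deadline obliges it to tell the sponsor. The same holds for a type 3a bleed defined by a haemoglobin drop, if the investigator judges it non-serious; there a single event is enough to trigger review. The documents also do not say who keeps the running count or how often the eCRF is checked for it.

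At stake is the time during which new participants are still randomised and the DSMB has not been called. This matters most early on. The first scheduled DSMB review waits until 20 participants have completed 6 weeks of treatment, so until then the ad hoc trigger is the only DSMB review the protocol provides for type 2 bleeds.

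**Working it through.** The documents state no reporting delay and no operating characteristic for the trigger, so there is no figure of the plan's own to reproduce. The permitted lag can be built from the schedule.

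**Inputs**
- Nominal visits at weeks 0, 1, 4, 8, 12 and 18, that is days 0, 7, 28, 56, 84 and 126 (Protocol section 2.0).
- Windows: week 1 on days 1 to 13 (section 9.3); "weeks 4, 8 and 12 to be done +/- 2 weeks of scheduled visit date" (section 2.0, note c), giving days 14–42, 42–70 and 70–98; week 18 up to 2 weeks late, giving days 126–140.
- eCRF entry: 7 days after the visit (section 11.1.1).

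**Formula.** For a bleed the site learns of just after one visit, where that contact is not itself a study visit: maximum lag from site awareness to eCRF entry = gap to the next visit + 7 days.

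| Interval | Nominal gap | Lag | Widest gap | Lag |
|---|---|---|---|---|
| Week 0–1 | 7 − 0 = 7 | 14 days (2.0 wk) | 13 − 0 = 13 | 20 days (2.9 wk) |
| Week 1–4 | 28 − 7 = 21 | 28 days (4.0 wk) | 42 − 1 = 41 | 48 days (6.9 wk) |
| Week 4–8 | 56 − 28 = 28 | 35 days (5.0 wk) | 70 − 14 = 56 | 63 days (9.0 wk) |
| Week 8–12 | 84 − 56 = 28 | 35 days (5.0 wk) | 98 − 42 = 56 | 63 days (9.0 wk) |
| Week 12–18 | 126 − 84 = 42 | 49 days (7.0 wk) | 140 − 70 = 70 | 77 days (11.0 wk) |

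The 9-week figure needs an 8-week gap between visits. The windows allow it, but section 8.1 dispenses only one month of drug at a time, so 5 weeks is the firmer on-treatment ceiling.

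**Typical rather than worst case.** If bleeds fall evenly over the 12 treatment weeks and visits are nominal, the mean wait to the next visit is (1² + 3² + 4² + 4²) / (2 × 12) = 42/24 = 1.75 weeks. With the eCRF week this makes 2.75 weeks. A simulation agrees. It assumed 60 participants accrued over 52 weeks, 10 to 30% of them with one type 2 bleed on treatment, each reported at the next scheduled visit and entered after the full 7 days. The fourth report trailed the fourth event by a mean of 2.7 to 2.8 weeks with nominal visits and about 3.3 weeks with visits spread over their windows.

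**When the site first hears at the visit.** Take a bleed on day 29 first mentioned at week 8. With the visit on day 56, entry is due by day 63: 34 days in all, of which 27 pass before the site knows. With the visit on day 70, entry is due by day 77: 48 days, of which 41 precede awareness. For a bleed on day 85 first mentioned at week 18, the totals are 133 − 85 = 48 and 147 − 85 = 62 days, of which 41 and 55 precede awareness. In each case the eCRF rule adds only 7 days. Reporting from awareness would save about 6 of them, taking 24 working hours as roughly one day.

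**Recruitment during a lag.** The accrual period is not stated. Participants randomised in L weeks = 60 / accrual weeks × L. For L of 5 and 9 weeks this gives about 12 and 21 over an assumed 26 weeks, 6 and 10 over 52 weeks, and 3 and 5 over 104 weeks.

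**The case against.** The best reply is that sites will usually act faster than the text requires. A type 2 bleed is by definition actionable. Section 10.3.2 asks for a haemoglobin sample when a clinically significant bleed is suspected, and section 10.3.2.2 recommends at least weekly monitoring of the type 2 bleeds it covers. If such a contact counts as a study visit, eCRF entry is due within a week of it. This stands as a limit on the size of the lag, but the text does not settle whether an unscheduled contact counts. It also cuts the other way: the more promptly a site learns of a bleed, the longer it may hold that knowledge before a deadline applies.

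The Manual of Operations and the DSMB operating guidelines were not supplied and could contain a faster route. That stands too; the point is confined to the protocol and SAP.

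A reader might infer more than the documents support, in four ways:
- That the eCRF rule by itself makes every count 5 to 9 weeks late. It does not. For a bleed first raised at a scheduled visit, most of the lag precedes site awareness and no reporting rule removes it.
- That the ad hoc trigger is no faster than the 8-weekly reviews. Scheduled reviews can count only bleeds already reported, so they carry the same lag and then add their own wait.
- That participants are dosed for longer because of the delay. Under section 18.0 those already randomised stay on treatment after the trigger.
- That most type 2 bleeds are non-serious. The documents give no proportion, and the medical-importance criterion will capture some.

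**Conclusion.** The point holds in a limited form. A bleed that counts towards the section 18.0 trigger but is not an SAE has no deadline for reaching the sponsor beyond routine eCRF entry after a study visit. For a bleed known to the site between visits, the ceiling on the lag is 5 weeks on treatment with nominal visits, 9 weeks at the widest windows, and 7 to 11 weeks in phase 2. A typical on-treatment lag under the same reading is about 3 weeks. The figures assume that the between-visit contact is not a study visit, that no visit is missed, and that the full eCRF week is used.

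The trigger is not breached, because it counts reports; it is slowed relative to the bleeds themselves. The consequence is a later recruitment pause and a later ad hoc review. The change should be made, because the protocol already gives quicker reporting to several event types that feed no stopping or pausing rule.

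**What to change.** In section 11.2.1, or beside 11.4.1, require every BARC type 2, 3 or 4 bleed to be sent to the coordinating centre by the SAE route from the time the site becomes aware of it, whether or not it meets the SAE definition. Type 5 bleeds are fatal and so are SAEs already. In section 18.0, state that the count of four type 2 events or one type 3 event is kept from these reports, and name who keeps it.

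This changes reporting only. The trigger thresholds and the handling of study drug after a bleed are untouched. For a bleed known between visits, it replaces a permitted lag of up to 5 weeks (nominal) or 9 weeks (widest windows) on treatment with 24 working hours. For a bleed first heard of at a visit, it saves about 6 days.

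The cost is one sentence in each of two sections and a few more event forms in a 60-participant trial. If the Manual of Operations already sets such a route, a cross-reference to it in sections 11 and 18.0 would be enough.

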11.2 Serious Adverse Event (SAE)

The definition of a SAE is any untoward medical occurrence that at any dose:

- results in death,
- is life-threatening,
(Note: the term “life-threatening” in the definition of “serious” refers to an event/reaction in which the participant was at risk of death at the time of event/reaction; it does not refer to an event/reaction which hypothetically might have caused death if it were more severe)
- requires in-patient hospitalisation (≥ 24 hours) or prolongation of existing hospitalisation,
- results in persistent or significant disability/incapacity,
- is a congenital anomaly/birth defect
or
- is a medically important event or reaction

Medical and scientific judgment should be exercised in deciding whether other situations should be considered serious e.g. important medical events that may not be immediately life-threatening or result in death or hospitalisation but may jeopardise the participant or may require intervention to prevent one of the outcomes listed in the definition above. Examples of such events are intensive treatment in an emergency room or at home for allergic bronchospasm, blood dyscrasias or convulsion that does not result in hospitalisation, or development of drug dependency or drug abuse.

Where SAEs are related to the drug, they may be referred to as Serious Adverse Drug Reactions.

11.2.1 Reporting Serious Adverse Events

SAEs should be collected following the participant’s written consent to participate in the study. All serious adverse events (SAEs) must be reported within 24 working hours after the SAE occurs or from the time when the study investigator first becomes aware of the SAE whether or not there is a suspected causal relationship to the study drug.

SAEs must be reported to the Kirby Institute by telephone, email or fax. The appropriate Serious Event form should be used. The Project team in conjunction with the Medical Officer will review all SAEs for completion and accuracy. Immediate reports should be followed promptly by detailed, written follow-up reports when all information is not included in the initial report. The immediate and follow up reports should identify participants by unique code numbers assigned to study participants rather than personal identification. Such reports must be supported by copies of de-identified relevant laboratory and diagnostic tests and further information as it becomes available. Copies of all x-rays and other imaging related to the event must be sent to the Sponsor, as well as all discharge summaries should the participant have been hospitalised. For deaths, the Principal Investigator will supply the sponsor and the IRB/IEC with any additional requested information (e.g. death certificate, autopsy reports and medical reports).

Line listings of SAEs occurring during the study will be distributed to all sites by the Kirby Institute on a quarterly basis. Study treatment group will not be provided.

The investigator must also comply with all applicable ethical and regulatory requirement/s relating to the reporting of serious adverse events.

Any serious adverse event that is ongoing at the post-study follow-up visit must be followed until resolution or until the event stabilises (for those events that will not resolve).

